6.6.3. Context and rationale for study exclusion criteria.....	14
6.6.4. Context and rationale for exposure(s) of interest.....	14
6.6.5. Context and rationale for outcome(s) of interest.....	15
6.6.6. Context and rationale for follow up.....	17
6.6.7. Context and rationale for covariates	17
6.7. Data analysis	22
6.7.1. Context and rationale for analysis plan	22
6.8. Study size and feasibility	32
7. Limitation of the methods.....	31
8. Protection of human subjects	31
9. References	32
10. Appendices	34
10.1. CONSORT diagrams	34
10.2. Covariate balance figures	37
10.3. Sample size/power calculations.....	40
10.4. Additional Figures and Tables	41

2. Abstract

This trial emulation study aims to emulate the PALOMA-2 trial (NCT01740427) using real-world specialty oncology electronic health records data and to investigate the concordance between the trial's original and the emulated treatment effect estimate on overall survival (OS). PALOMA-2 was a Phase III, randomized, double-blind study evaluating the efficacy and safety of palbociclib (125 mg orally, once daily for 21 days followed by 7 days off) in combination with letrozole (2.5 mg orally, once daily, continuously) versus placebo plus letrozole in postmenopausal women with estrogen receptor-positive (ER+), human epidermal growth factor receptor 2-negative (HER2-) advanced breast cancer who had not received prior systemic treatment for their advanced disease.

3. Amendments and updates

Version date	Version number	Section of protocol	Amendment or update	Reason
June 11, 2025	V1.0	NA	Initial version	NA
August 18, 2025	V1.1	4. Rationale and background 5. Research question and objective 6. Research methods	Refinement of text based on FDA feedback	NA
January 31, 2026	V1.2	6. Study design diagram	Study design diagram updated to explicitly reflect data vendor proprietary business rules for line-of-therapy assignment, exposure assessment window, and calendar year alignment; diagram now accounts for date imprecision between metastatic diagnosis and line of therapy initiation	To improve transparency and consistency with vendor-specific line-of-therapy definitions and real-world data timing constraints
		Table 5 (Covariates)	Added explicit covariate assessment window for c_number_met_sites	To align covariate derivation with vendor business rules governing line of therapy and metastatic timing

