Eligibility criteria	
 • Women aged ≥ 18 years with diagnosis of breast cancer • Histologically or cytologically confirmed adenocarcinoma of the breast • Locoregionally recurrent or metastatic disease not amenable to curative resection/radiotherapy • ER-positive status • HER2-negative status • Postmenopausal status • No prior systemic therapy for advanced/metastatic ER+ disease • Measurable disease per RECIST v1.1 or bone-only disease confirmed by imaging • WHO/ECOG performance status 0 or 1 	
 • Female aged ≥ 18 years at treatment initiation with a diagnosis of breast cancer • Diagnosis of breast adenocarcinoma via histology/pathology records • Evidence of metastatic or recurrent disease • Documentation of ER-positive (or -missing) status • Documentation of HER2-negative (or -missing) status • N/A • No systemic anti-cancer therapy* following initial record indicating metastatic disease and prior to index date • N/A • WHO/ECOG performance status of 0 or 1 within 90 days of index date 	
 • If ER is missing and a patient received the exposures of interest, then ER is likely to be positive given the alignment with the indication for the exposures of interest • If HER2 is missing and a patient received the exposures of interest, then HER2 is likely to be negative given the alignment with the indication for the exposures of interest • Although not directly captured in RWD, it is likely to be fulfilled given the alignment with the indication for the exposures of interest • It is reasonable to assume that all patients in RWD had evidence of disease if they received treatment; additionally OS primary endpoint does not require measurable disease

- No symptomatic, life-threatening visceral disease (e.g., massive effusions, >50% liver involvement)

- N/A

- No active or symptomatic CNS metastases

- Record of CNS metastases prior to or on index date

- No prior treatment with CDK4/6 inhibitors

- Exclude patients with prior CDK4/6 inhibitor exposure

- No recurrence during or within 12 months of adjuvant non-steroidal AI (anastrozole or letrozole)

- Treatment with letrozole or anastrozole ≤ 12 Months prior to date of metastatic diagnosis

- No other malignancy within 3 years

- No prior record of non-breast malignancy within 3 years

- N/A

- Restriction to the time period 2015-2022

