6.6. Setting

6.6.1. Context and rationale for definition of time 0 (and other primary time anchors) for entry to the study population

Time 0 in this database study is defined as the date a patient initiated palbociclib plus letrozole (exposure) or letrozole alone (comparator) as part of their 1L systemic antineoplastic treatment for advanced/metastatic adenocarcinoma of the breast. This aims to emulate the date of randomization and cohort entry in the RCT (the time from randomization to first dose is not reported in the [clinicaltrials.gov study report](https://clinicaltrials.gov/study/NCT02420417) or the trial articles).

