Socio-economic status	dem_ses	edbx_get_demographics()	Socioeconomic status (SES) index based on residence area of patient. Not available in EDB3 and EDB4.	Nominal (from '1 - Lowest SES' through '5 - Highest SES')	[-inf;0]
Smoking	c_smoking_history	edbx_get_demographics()	History of current or former (= TRUE) or never (= FALSE) smoking on or anytime before index date; if there are multiple records per patient, any evidence of former/current smoking is prioritized. IN EDB1, "smoking history" is not available for breast cancer.	Binary logical (TRUE, FALSE)	[-inf;0]
ECOG	c_ecog	edbx_get_ecog()	ECOG performance status measured closest to index date within assessment window. In	Nominal (0, 1, 2, 3, 4); modelled as ordinal numeric in ROPRO ¹⁰ ; due to I/E	[-90;0]

Characteristic	Harmonized analysis variable name	R function to derive covariate (see pdf in appendix)	Details ¹	Variable encoding	Assessment window
			case of ties, the lower ECOG value is selected	criteria ECOG is modelled as a binary (0, 1) covariate	
Stage	c_stage_initial_dx	edbx_get_diagnosis_solid()	AJCC summary group stage at initial diagnosis	Ordinal numeric (from 0 to IV with sub-categories, e.g., IA1) ¹⁰	[-inf;0] at initial diagnosis of primary cancer
De novo metastatic status	c_de_novo_mets_dx	edbx_get_diagnosis_solid()	Evidence of presence of one or multiple metastases at/before initial diagnosis	Binary logical (TRUE, FALSE)	[-inf;0] at initial diagnosis of primary cancer
Number of metastatic sites	c_number_met_sites	edbx_get_diagnosis_solid()/edbx_get_number_met_sites_solid()	Number of metastatic sites for a given patient before/on index date	Integer	[-inf;X]; Proprietary business-rule-based covariate assessment window
Time between initial diagnosis to index date	c_time_dx_to_index	edbx_get_diagnosis_solid()	Time in days between initial diagnosis to index date. Quartiles will be used because there may be “negative” times intervals due to date imprecision of the lines of therapy.	Categorical (quartiles)	[-initial dx;0]
Time between earliest evidence of a metastatic and index date	c_time_met_dx_to_index_quartiles	edbx_get_diagnosis_solid()	Time in days between earliest evidence of a metastatic diagnosis and index date. Quartiles will be used because there may be “negative” times intervals due to date imprecision of the lines of therapy.	Categorical (quartiles)	[met dx;0]

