Exposure palbociclib plus letrozole; 125 mg, orally once daily on Day 1 to Day 21 of every 28-day cycle followed by 7 days off treatment; in combination with Letrozole, 2.5 mg, orally once daily (continuously).
Comparisons placebo plus letrozole; Placebo orally once daily on Day 1 to Day 21 of every 28-day cycle followed by 7 days off treatment;
Emulated outcome Overall survival (secondary objective in original trial)

Key Inclusion/Exclusion Criteria						Comment
Criteria	RCT eligibility criteria (taken from the original trial protocol)	Clinical relevance	Emulation [EDB1]	Emulation [EDB3]	Emulation [EDB4]	
Inclusion	Adult women, aged at least 18 years.	Relevant	Possible	Possible	Possible	To protect privacy, most databases only provide month- or year-level granularity of dates
Inclusion	Adenocarcinoma of the breast with locoregionally recurrent or metastatic disease not amenable to resection or radiation therapy with curative intent and for whom chemotherapy is not clinically indicated	Relevant	Possible	Possible	Possible	Identify patients with metastases
Inclusion	Documentation of histologically or cytologically confirmed diagnosis of estrogen-receptor positive (ER+) breast cancer based on local laboratory results.	Relevant	Possible	Possible	Possible	Keep if ER+ or missing.
Inclusion	Previously untreated with any systemic anti-cancer therapy for their locoregionally recurrent or metastatic ER+ disease.	Relevant	Possible	Possible	Possible	Assuming that any therapies for advanced disease occurred following metastasis was recorded in the data
Inclusion	Postmenopausal women defined as women with: - Prior bilateral surgical oophorectomy, or - Medically confirmed post-menopausal status defined as spontaneous cessation of regular menses for at least 12 consecutive months or follicle-stimulating hormone (FSH) and estradiol blood levels in their respective postmenopausal ranges with no alternative pathological or physiological cause.	Relevant	Limited	Limited	Limited	Can define based on age

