Exclusion 1	HER2-positive breast cancer	$[-\infty; 0]$	Any HER2+ status prior to or on index date	Any HER2+ status prior to or on index date	Any HER2+ status prior to or on index date	If HER2 is missing and a patient received the exposures of interest, then HER2 is likely to be negative given the alignment with the indication for the exposures of interest	edbx_get_her2()
Exclusion 2	Patients with advanced, symptomatic, visceral spread, that are at risk of life-threatening complications in the short term (including patients with massive uncontrolled effusions [pleural, pericardial, peritoneal], pulmonary lymphangitis, and over 50% liver involvement).	NA	NA	NA	NA	This is a safety criterion for the trial and less relevant to real-world treatment setting, given that patients received treatments of interest	
Exclusion 3	Known active uncontrolled or symptomatic CNS metastases, carcinomatous meningitis, or leptomeningeal disease as indicated by clinical symptoms, cerebral edema, and/or progressive growth. Patients with a history of CNS metastases or cord compression are eligible if they have been definitively treated with local therapy (eg, radiotherapy, stereotactic surgery) and are clinically stable off anticonvulsants and steroids for at least 4 weeks before randomization.	$[-\infty; 0]$	Record of CNS metastases prior to or on index date	Record of CNS metastases prior to or on index date	Record of CNS metastases prior to or on index date		edbx_get_diagnosis_solid()
Exclusion 4	Prior neoadjuvant or adjuvant treatment with a non-steroidal aromatase inhibitor (ie, anastrozole or letrozole) with disease recurrence while on or within 12 months of completing treatment.	[MBC-365; MBC-1]	Treatment with letrozole or anastrozole ≤ 12 months from MBC	Treatment with letrozole or anastrozole ≤ 12 months from MBC	Treatment with letrozole or anastrozole ≤ 12 months from MBC		
Exclusion 5	Prior treatment with any CDK4/6 inhibitor.	$[-\infty; -1]$	Prior treatment with ribociclib, palbociclib, abemaciclib	Prior treatment with ribociclib, palbociclib, abemaciclib	Prior treatment with ribociclib, palbociclib, abemaciclib		
Exclusion 6	Major surgery, chemotherapy, radiotherapy, any investigational agents, or other anti-cancer therapy within 2 weeks before randomization. Patients who received prior radiotherapy to 25% of bone marrow are not eligible independent of when it was received (see Appendix 4).	NA	NA	NA	NA		Proxied by 1st line therapy inclusion

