Exclusion 7	Diagnosis of any other malignancy within 3 years prior to randomization, except for adequately treated basal cell or squamous cell skin cancer, or carcinoma in situ of the cervix.	$[-1095; 0]$	Record of cancer diagnosis within 1095 days prior to or on index day	Record of cancer diagnosis within 1095 days prior to or on index day	Record of non-index cancer treatment within 1095 days prior to or on index day	No diagnosis table for EDB4 available	
Exclusion 8	Record of systemic anticancer therapy other than exposure/comparator on index date	$[0; 0]$	Exclusion if treatment is any other than palbociclib-plus-letrozole or letrozole alone	Exclusion if treatment is any other than palbociclib-plus-letrozole or letrozole alone	Exclusion if treatment is any other than palbociclib-plus-letrozole or letrozole alone		

MBC = first metastatic breast cancer date

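### In EDB1 and EDB3, Exclusion 4 as written removes patients for their own index letrozole when the index date precedes the recorded metastatic date, although Table 5 expects to keep them

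*Combined protocol and SAP*

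**What the plan says.** The trial criterion, reproduced in the Exclusion 4 row of Excel appendix Table 2, is restricted to "Prior neoadjuvant or adjuvant treatment with a non-steroidal aromatase inhibitor (ie, anastrozole or letrozole) with disease recurrence while on or within 12 months" of completing it. The operational cells for all three databases shorten this to "Treatment with letrozole or anastrozole ≤ 12 months from MBC". The time column sets the window at MBC minus 365 days to MBC minus 1 day, and the table's footnote gives "MBC = first metastatic breast cancer date". Table 2 in Section 5 confirms that the window runs backwards: "Treatment with letrozole or anastrozole ≤ 12 Months prior to date of metastatic diagnosis".

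Section 6.6.1 sets time 0 at the start of palbociclib plus letrozole or of letrozole alone, so letrozole is an index drug in both arms.

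Table 5 (Section 6.6.7) handles time from metastatic diagnosis to index in quartiles because there may be negative "times intervals due to date imprecision of the lines of therapy". The V1.2 entry in Section 3 acknowledges the same issue for the design figure: "diagram now accounts for date imprecision between metastatic diagnosis and line of therapy initiation".

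Two statements point the other way. Table 1 (Section 5) says that line-of-therapy classification in EDB1 and EDB3 begins only after the advanced or metastatic diagnosis. Section 6.6.4 requires the EDB4 index treatment to be no earlier than the recorded metastasis.

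**The concern.** Exclusion 4 is meant to catch recurrence on, or soon after, an adjuvant aromatase inhibitor. Its window is tied to MBC alone and its drug list includes the study drug. It therefore cannot tell adjuvant letrozole from first-line letrozole whose start happens to be dated before MBC. Table 5 treats the second situation as a dating artefact to be modelled; Exclusion 4 treats it as grounds for removal. Both cannot be applied as written to the same patient.

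What is at stake is who enters the primary cohort. Eligible first-line patients could be dropped because of how two dates were recorded, and a second team following the text would build a different cohort from one following Table 5.

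**Working it through.** **Inputs**
- Exclusion 4 window: MBC−365 to MBC−1, any letrozole or anastrozole (Excel appendix Table 2).
- Index: start of a letrozole-containing regimen in both arms (Section 6.6.1).
- Negative MBC-to-index intervals: possible (Table 5).
- Matched-set events and power at HR 0.92: 1021 and 0.27 in EDB1; 331 and 0.11 in EDB3 (Section 10.3; alpha 0.05, 50% exposed).

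**1. Date logic.** Let d = index − MBC in days. The index letrozole starts on day MBC + d, so its start lies in the window exactly when −365 ≤ d ≤ −1.

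| d (days) | index letrozole start in window? |
|---|---|
| −400 | no (but continuing use would overlap the window) |
| −365 | yes |
| −30 | yes |
| −1 | yes |
| 0 | no |
| +30 | no |

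The result is the same in either arm.

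**2. Can d be negative?** In EDB4, no: Section 6.6.4 rules it out. In EDB1 and EDB3, Table 5 says it may be, whereas Table 1 implies it should not be. These two statements conflict, so Table 1 does not settle the matter.

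**3. Does other text rescue the rule?** Exclusion 5 (prior CDK4/6 inhibitor) ends the day before index. Exclusion 8 (other therapy on the index date) exempts the study regimens by name. Exclusion 4 has neither safeguard.

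**4. Precision.** The plan's power figures reproduce with the two-sided Schoenfeld formula, power = Φ(√(D × 0.25) × |ln 0.92| − 1.96):
- EDB1: √(1021 × 0.25) × 0.0834 = 1.332, and Φ(1.332 − 1.96) = 0.265, against 0.27 stated.
- EDB3: √(331 × 0.25) × 0.0834 = 0.758, and Φ(0.758 − 1.96) = 0.115, against 0.11 stated.

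No count of affected patients is given, so assume that the rule removed a share x of otherwise matched patients and events. Restored events are D/(1 − x):

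| assumed x | EDB1 events, power | EDB3 events, power |
|---|---|---|
| 1% | 1031, 0.267 | 334, 0.116 |
| 5% | 1075, 0.277 | 348, 0.119 |
| 10% | 1134, 0.289 | 368, 0.123 |
| 15% | 1201, 0.303 | 389, 0.128 |

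Power barely moves.

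**5. How common could negative gaps be?** This is an assumption-only range. Suppose the true gap from MBC to index is exponential with rate λ = ln 2/median, true dates fall evenly over a 30.4-day month, and one of the two dates is recorded at mid-month (day 14.5). The share with index before MBC is then [t − (1 − e^(−λt))/λ]/30.4, with t = 14.5 if MBC is the coarse date and t = 30.4 − 14.5 = 15.9 if index is.

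Example, median 14 days, t = 14.5: λ = 0.0495, e^(−0.718) = 0.488, and (14.5 − 0.512/0.0495)/30.4 ≈ 0.137.

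| median gap (days) | MBC coarse | index coarse | both at mid-month |
|---|---|---|---|
| 7 | 22% | 26% | 0% |
| 14 | 14% | 16% | 0% |
| 30 | 7% | 9% | 0% |
| 60 | 4% | 5% | 0% |

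The last column is zero because two dates rounded in the same way cannot reverse their order. The range therefore runs from nothing to about a quarter depending on choices the documents do not fix. In this model no negative gap exceeds 15.9 days.

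**The case against.** The best defence is that the trial criterion stands in the same row, so the operational cell is shorthand for it, and letrozole in a curated first metastatic line is not prior adjuvant treatment. That is a fair account of the intent. It does not change the operational rule, which drops the adjuvant qualifier.

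Second, the cohorts have already been assembled and matched (1812 in EDB1, 610 in EDB3), and Table 5 still provides for negative intervals, which would be largely unnecessary had Exclusion 4 removed those patients. The code may already cap the window. The code, the design figure and the attrition diagrams cannot be seen, so this stands as a possibility. If it is so, the written rule misdescribes what was done and still needs correcting.

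A reader might infer more than the documents support:
- **A sizeable loss.** Table 5 says only that negative intervals may occur. It attributes them to line-of-therapy dates, and mid-month imputation is documented only for dates of death. The remark that "To protect privacy, most databases only provide month- or year-level granularity of dates" is a general comment in the age row. The gap medians above have no source.
- **Bias between arms.** Both arms take letrozole. Differential loss would require date imprecision that differs by arm, which nothing in the documents shows.
- **An emptied lowest quartile.** Quartiles formed on the analysed cohort are redrawn after exclusions, and no text says they are formed before.
- **All three databases affected.** EDB4 is not.

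A further objection bears on the remedy. Exempting index-line letrozole at any gap up to 365 days goes too far: letrozole begun 200 days before MBC is hard to call a dating artefact and may be the adjuvant exposure that the criterion targets. This stands, and the fix is limited accordingly.

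**Conclusion.** The conflict is real and lies in the written rules. For EDB1 and EDB3, a patient with index 1 to 365 days before MBC is kept by Table 5 and removed by Exclusion 4, in either arm. It follows from the date definitions alone and needs no distributional assumption.

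Its practical size is undetermined. The number affected could be zero, the gap sizes are not reported, and a difference by arm is neither shown nor excluded. Power is essentially unaffected under assumed losses of up to 15%. It should not be read as evidence that patients were in fact deleted or that the hazard ratio is biased. It is worth correcting because it governs entry to both primary-analysis cohorts and the correction is cheap.

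**What to change.** 1. **Exclusion 4, EDB1 and EDB3:** end the look-back the day before the earlier of MBC and index, so that only letrozole or anastrozole given before the index line counts. Starting it 365 days before that same date keeps its length.
2. **Limit the exemption:** disregard index-line letrozole only when the negative gap lies within the vendor's line-of-therapy date-imprecision window. Beyond that, keep the MBC-anchored rule. If the window is proprietary, state that such a limit was applied in the code.
3. **Reconcile the text:** align Table 1 (lines begin after metastatic diagnosis), Table 5 (intervals may be negative) and Exclusion 4. If the code already caps the window, say so.
4. **Report:** for EDB1 and EDB3, by arm, give the number of patients with index before MBC, the distribution of the gap, and the number the present rule would remove.

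The cost is one table cell, about one line of cohort code, and a rerun of the attrition; if membership changes, imputation and matching must be rerun as well. The downside is that a few patients with true recent adjuvant letrozole and a misdated line may be retained. The limit in item 2 restrains this, and the counts in item 4 show how many patients are in question.
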